11.5.2 Safety endpoints

Adverse events

All information obtained on adverse events will be displayed by initial and administered dose and patient. For reporting purposes, the main focus will be on treatment emergent adverse events (TEAEs). Treatment emergent AEs are defined as events starting on or after the first dose of study drug that were absent pre-treatment, or events present prior to the first dose but increased in severity after the first dose. TEAEs will be summarized in appropriate summary tables and in Parts 2 & 3, also displayed in stacked bar charts. All adverse events will be presented in listings.

Vital signs

All vital signs data will be listed by treatment, patient, and visit/time and if ranges are available abnormalities (and relevant orthostatic changes) will be flagged. Summary statistics will be provided by scheduled visit, part, and treatment where appropriate. Individual blood pressure and pulse will be displayed in panel plots, while individual length and weight data will be displayed in spaghetti plots with US Center for Disease Control and Prevention (CDC) percentiles relative to age at evaluations (in months).

ECG evaluations

All ECG data will be listed by treatment, patient and visit/time, abnormalities will be flagged. Summary statistics will be provided by scheduled visit, part, and treatment where appropriate. Individual ECG data will be displayed in panel plots.

Clinical laboratory evaluations

All laboratory data will be listed by treatment, patient, and visit/time and if normal ranges are available abnormalities will be flagged. Summary statistics will be provided by scheduled visit, part and treatment where appropriate.

In addition, shift tables will be provided for all parameters to compare a patient's baseline laboratory evaluation relative to the post-baseline values. Liver enzyme data will be summarized according to newly occurring abnormality criteria, as well as some standard graphs for this data.

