The safety cutoff applies to safety analyses only. The only exception to this are serious adverse events and deaths. Any SAEs occurring after the 30 days period, where a causal relationship to study treatment is suspected, will be reported. All deaths will be reported irrespective of safety cutoff.

In general, treatment emergent AEs are defined as events starting after the first dose of study drug that were absent pre-treatment, or events present prior to the first dose but increased in severity after the first dose. This assumes the same AE with increased severity is properly entered as a separate record in the database with start date being the date when severity increases and that a second AE with same severity won't be entered before the same AE is resolved.

For any other safety analyses based on post-baseline abnormalities compared to baseline (i.e. ECGs, vital signs, etc.), where either of the results is not available, the '**missing**' category will be included to avoid any abnormalities being overlooked.

When showing values over time, for subjects who prematurely discontinued the study, study completion visit assessments will be displayed as if they had occurred at the next scheduled visit.

The eGFR is calculated using the MDRD formula. $eGFR [mL/min/1.73 m^2] = 175 \times (\text{serum Creatinine [umol/L]/88.4}) - 1.154 \times (\text{age [years]}) - 0.203 \times (0.742 \text{ if female}) \times (1.212 \text{ if African American})$ ([Levey et al. 2007](#)).

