2.8.2 Adverse events (AEs)

An adverse event (AE) is any untoward medical occurrence (i.e., any unfavorable and unintended sign [including abnormal laboratory findings], symptom or disease) in a subject or clinical investigation of a subject after providing written informed consent for participation in the study. That means that a subject can report AEs before having started study drug. For reporting purposes, the main focus will be on treatment emergent adverse events (TEAEs). Treatment emergent AEs are defined as events starting on or after the first dose of study drug that were absent pre-treatment, or events present prior to the first dose but increased in severity after the first dose (based on the MedDRA lower level term (LLT)). TEAEs are included up to the safety cutoff (as defined in [Section 2.1.1](#)). Except for serious TEAEs and death, only TEAEs up to and including safety cutoff (as defined in [Section 2.1.1](#)) will be included in the analyses. For serious TEAEs a modified safety cutoff is used (as defined in [Section 2.1.1](#)). TEAEs will be assigned to Part 3 if the start date is on/after the first visit date of Part 3 (see section 2.1.1). All deaths will be included, regardless of safety cutoff.

AEs will be reported by primary system organ class (SOC) and preferred term (PT) according to the Medical Dictionary for Regulatory Activities (MedDRA). The MedDRA version used for reporting the study will be described in a footnote.

The number and percentage of subjects reporting any TEAEs will be summarized by primary SOC, preferred term, maximum CTCAE grade (individual, as well as Grade 3 and above combined) and treatment group (Parts 2 & 3). Missing CTCAE grade will not be imputed. Separate summaries will be provided for serious TEAEs, drug related TEAEs, TEAEs leading to permanent discontinuation of study drug and most common TEAEs (10% in any group). Furthermore, exposure-adjusted incidences will be reported in an AE overview table, for all AEs in a table by system organ class and preferred term by part, and similarly for serious AEs.

If a subject reported more than one adverse event within the same primary system organ class, the subject will be counted only once with the maximum CTCAE grade at the system organ class level, where applicable.

All AEs will be presented in listings.

The following graphs will be displayed:

- Bar charts of MedDRA system organ classes - crude incidences

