5.1.2 AE and concomitant medication date imputation

Incomplete start date or end date of an adverse event or concomitant medication taken will be handled by following rules:

Table 5-1 Imputation of start dates (AE, CM)

Missing Element	Rule
day, month, and year	
• No imputation will be done for completely missing dates
day, month	
• If available year = year of study treatment start date then
◦ If end date contains a full date and end date is earlier than study treatment start date then set start date = 01JanYYYY◦ Else set start date = study treatment start date.• If available year > year of study treatment start date then 01JanYYYY• If available year < year of study treatment start date then 01JulYYYY
day	
• If available month and year = month and year of study treatment start date then
◦ If end date contains a full date and end date is earlier than study treatment start date then set start date= 01MONYYYY.◦ Else set start date = study treatment start date.• If available month and year > month and year of study treatment start date then 01MONYYYY• If available month and year < month year of study treatment start date then 15MONYYYY

Table 5-2 Imputation of end dates (AE, CM)

Missing Element	Rule (* = min(death date, safety cutoff date, withdrawal of consent date))
day, month, and year	
• Completely missing end dates (incl. ongoing events) will be imputed by the end date of the on-treatment period*

Missing Element	Rule (*= $\min(\text{death date, safety cutoff date, withdrawal of consent date})$)
day, month	
• If partial end date contains year only, set end date = earliest of 31DecYYYY or end date of the on-treatment period *
day	
• If partial end date contains month and year, set end date = earliest of last day of the month or end date of the on-treatment period*

Notice if imputed end date is less than the start date (if complete), use the start date as the imputed end date.

Any AEs and ConMeds with partial/missing dates will be displayed as such in the data listings.

For adverse events and any prior or concomitant medication, to decide whether the event or medication was prior or post-dosing is carried out as follows:

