- If start date and time are not missing, then report as post-dosing if start date and time > dosing start date and time
- If start date is available, but not start time, then report as post-dosing if start date > dosing start date. This means that all events occurring on the dosing start day (even if they occurred prior to it) will be considered as post-dosing – similarly for medications, will be considered as concomitant.
- If both start date and time are missing, both adverse events and medications will be defined as being post-dosing.

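### SAP 5.1.2 makes an untimed adverse event on the first-dose day both pre-dosing and post-dosing, and SAP 2.1.1 and 2.8.2 disagree on whether such an event is treatment-emergent

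*SAP*

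**What the plan says.** SAP 5.1.2 ends with three bullets for adverse events and medications, introduced by the words "to decide whether the event or medication was prior or post-dosing is carried out as follows".

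- **First bullet (date and time known).** The event is post-dosing if its date and time are strictly later than those of the dosing start.
- **Second bullet (date known, time not).** The rule is "If start date is available, but not start time, then report as post-dosing if start date > dosing start date". The bullet then explains that "all events occurring on the dosing start day (even if they occurred prior to it) will be considered as post-dosing".
- **Third bullet (nothing known).** "If both start date and time are missing, both adverse events and medications will be defined as being post-dosing".

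Before these bullets, Table 5-1 completes partial start dates. Where the known year, or month and year, matches the start of treatment and no full end date falls before treatment, the instruction is "Else set start date = study treatment start date".

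The TEAE is defined three times. SAP 2.1.1, as a general statement, says "treatment emergent AEs are defined as events starting after the first dose of study drug". SAP 2.8.2, the section on adverse event analysis, says "Treatment emergent AEs are defined as events starting on or after the first dose of study drug". Protocol 11.5.2 says "Treatment emergent AEs are defined as events starting on or after the first dose of study drug that were absent pre-treatment". The SAP does not say whether the TEAE flag is derived from the 5.1.2 bullets or directly from one of these definitions.

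**The concern.** The operator in the second bullet and the sentence that explains it give opposite answers for one day, the day of first dose. A programmer who follows the symbol and one who follows the sentence will build different data sets. The main text does not settle the matter, because 2.1.1 and 2.8.2 also differ on that day.

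SAP 2.8 rests the safety assessment mainly on adverse event frequencies, and safety is the primary objective of Parts 2 and 3. SAP 2.1 hands the analysis to an outside vendor, so the written rule is what will be coded. An event that begins on the day a child first receives the drug is one that a safety table should not lose through a coding choice.

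The untimed bullet may also apply often. Protocol 9.1.1 asks for the start and end dates of each event and does not mention a clock time. On the other hand, the Part 3 assignment rule in SAP 2.1.1 refers to a start date and time. The case report form is not in the documents, so how often times are missing cannot be settled.

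**Working it through.** There is no planned figure to reproduce. The check is one of logic, with untimed events placed on three days and each rule applied at date level. Events are taken as absent before treatment.

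| Untimed start | 5.1.2 operator (>) | 5.1.2 next sentence | 2.1.1 (after) | 2.8.2 and Protocol 11.5.2 (on or after) | With >= in 5.1.2 |
|---|---|---|---|---|---|
| Day before first dose | pre | pre | not TEAE | not TEAE | pre |
| Day of first dose | **pre** | **post** | **not TEAE** | **TEAE** | post |
| Day after first dose | post | post | TEAE | TEAE | post |

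The rules conflict on the day of first dose only. With >= the operator and its explanation agree in all three rows.

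**Partial dates.** Table 5-1 has nine start-date outcomes, and each was tested with > and with >=:

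- Everything missing: post-dosing under both, by the third bullet.
- Year only, same year as treatment start: if the event ended before treatment it goes to 1 January and is pre-dosing under both. **Otherwise it goes to the treatment start date: pre with >, post with >=.**
- Year only, later year: post under both. Earlier year: pre under both.
- Month and year, same month as treatment start: if the event ended before treatment it goes to the first of the month and is pre under both. **Otherwise it goes to the treatment start date: pre with >, post with >=.**
- Month and year, later month: post under both. Earlier month: pre under both.

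Two of the nine outcomes change, and this does not depend on the calendar date of first dose. It does assume that an imputed date counts as an available start date in the second bullet. The SAP does not say so for adverse events. For concomitant medication, SAP 2.4.2 does use imputed dates.

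**Direction.** Table 5-1 first sets aside events known to have ended before treatment and puts the remaining uncertain ones on the treatment start date. The third bullet counts events with no date as post-dosing. Both lean towards inclusion. With the strict sign, an event with no date at all is post-dosing while one known to have started on the first-dose day is not.

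**The case against.** The strongest reply is that the bullet resolves itself. Its second sentence states the intended result, and SAP 2.8.2 and Protocol 11.5.2 agree with it. SAP 2.1.1 is only a general statement, and 2.8.2 is the specific section. This stands as evidence of intent and is the main reason the point is minor. It does not remove the conflict, because the operator is the part most easily copied into a program.

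Four further limits stand:

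- **Worsening.** An event wrongly placed before dosing becomes a TEAE again if it increases in severity after the first dose. SAP 2.1.1 assumes that such an increase is entered as a separate record.
- **What is untouched.** All adverse events are listed and all deaths are reported (SAP 2.8.2). Concomitant medication has its own definition, which includes the day of first dose (SAP 2.4.2). The Part 1 dose-limiting toxicity analysis is not repeated (SAP 2.5).
- **Scope of 5.1.2.** It decides prior or post-dosing and does not mention TEAEs, so it may not feed the TEAE flag at all.
- **Extraction.** An inclusive sign lost from the PDF cannot be fully excluded. It is unlikely, since inclusive signs survive in SAP 2.1.1, 2.3.2 and 2.4.1.

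A reader might infer that the TEAE tables will be undercounted. The documents do not support that: if 2.8.2 is coded directly, the events stay in. Nor is the 5.1.2 operator the only route to losing them, since 2.1.1 applied at date level drops the same untimed events. A reader might also want a percentage. One of 13 treated patients is 1/13 = 7.7 points in a Parts 1 & 3 row, but that is the step for any single-patient error. Likewise, two of nine outcomes counts lines in a rule table, not events. Neither is an effect size.

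**Conclusion.** The contradiction in the second bullet of SAP 5.1.2 is real, and so is the difference between SAP 2.1.1 on one side and SAP 2.8.2 with Protocol 11.5.2 on the other. Confidence in this textual finding is high.

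The consequence is conditional. Untimed first-dose-day events leave the TEAE, serious-TEAE and special-interest tables if the flag is programmed from the literal 5.1.2 operator or from 2.1.1 at date level, and if they do not later worsen and return as a new record. Partial dates set to the treatment start date follow them only if imputed dates count as available. Even then a subject count changes only where the lost event was that patient's sole event in the row.

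The number of such events is not given and may be zero. Severity is minor: a drafting error with clear intent, worth correcting because it is cheap to correct and safety is the primary objective.

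**What to change.** 1. In the second bullet at the end of SAP 5.1.2, change > to >=, and state that the rule also applies to start dates imputed under Table 5-1.
2. In SAP 2.1.1, change the TEAE definition so that it includes a start on the first dose, to match SAP 2.8.2 and Protocol 11.5.2.
3. If SAP 2.8.2 is to refer to 5.1.2 for the TEAE flag, change the first bullet to >= as well. Otherwise a timed event at the exact dosing time would be pre-dosing under 5.1.2 but treatment-emergent under 2.8.2, and the cross-reference would carry that mismatch into the flag.
4. Check the programmed flag against the corrected text before the final tables are run.

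The cost is one or two operators, a few short phrases and one program check. The downside is that some events that began on the first-dose day before the dose will count as post-dosing. The SAP already accepts this in the same bullet.

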5.1.3 Values outside limits of quantification

For descriptive analyses of laboratory parameters [REDACTED] the following values will be imputed:

- LLOQ with $0.5 * \text{LLOQ}$
- ULOQ with $1.5 * \text{ULOQ}$

The frequency (n, %) of values either below the LLOQ or above the ULOQ will also be reported.

For PK analyses, other rules apply (see [Section 2.9.1](#)).

5.2 AEs coding/grading

Not applicable.

5.3 Laboratory parameters derivations

For each subject, the estimated creatinine clearance values (without collecting urine) will be calculated using the Cockcroft-Gault formula (as specified in [Table 5-3](#)). In these calculations, the body weight is the last measurement collected on or before the day when the subject takes the laboratory test and age should also be calculated based on the time when the subject takes the laboratory test.

If the creatinine value is collected in the unit $\mu\text{mol/L}$ (SI unit), it will be converted to mg/dL in order to use the formulas. The conversion is via the equation below:

- $\text{mg/dL} = 88.4 \mu\text{mol/L}$ (e.g., creatinine = 2.0 $\text{mg/dL} = 176.8 \mu\text{mol/L}$).

Table 5-3 Creatinine clearance calculation

Variable	Formula
Creatinine clearance [mL/min] using Cockcroft-Gault formula (Cockcroft and Gault 1976)	$= (140 - A) \times W / (72 \times C) \times G$ Where A is age [years] W is body weight [kg] C is the serum concentration of creatinine [mg/dL] G is a constant: G=1 for males and G=0.85 for females.

The estimated creatinine clearance will be included as one of the laboratory parameters.

5.3.1 Laboratory test groups and subgroups

On presenting lab results, grouping parameters by family will ease the review. [Table 5-4](#) below shows a possible set of lab parameters and their corresponding classification.

Table 5-4 Laboratory tests

Order	Laboratory Group Subgroups	Tests [SI unit]
1	Hematology	Absolute Basophils [10E9/L] Absolute Eosinophils [10E9/L] Absolute Lymphocytes [10E9/L] Absolute Monocytes [10E9/L] Absolute Neutrophils [10E9/L] Absolute other differentials [10E9/L] Basophils [%] Eosinophils [%] Hematocrit [1] Hemoglobin [g/L] Lymphocytes [%] Mean Platelet Volume [fL] Monocytes [%] Neutrophils [%] Other differentials [%] Platelet count direct [10E9/L] RBC [10E12/L] Reticulocytes [%] WBC (Total) [10E9/L]
2	Chemistry	Albumin [g/L] Alkaline Phosphatase [U/L] ALT [U/L] AST [U/L] Bicarbonate [mmol/L] Bilirubin (direct/conjugated) [umol/L] Bilirubin (indirect/unconjugated) [umol/L] Calcium [mmol/L]

Order	Laboratory Group Subgroups	Tests [SI unit]
		Chloride [mmol/L] Creatinine [umol/L] Free Thyroxine (FT4) [pmol/L] Glucose [mmol/L] hsCRP (high sensitive C-Reactive protein) [mmol/L] Potassium [mmol/L] Sodium [mmol/L] Thyroid hormones T4 [nmol/L] Thyroid stimulating hormone [mU/L] Urea [mmol/L]
3	Urinalysis	Bilirubin Dipstick test Blood Dipstick test Glucose Dipstick test Ketone Dipstick test Leukocytes Dipstick test Nitrite Dipstick test Protein Dipstick test Sediment - Casts Sediment - RBC Sediment - WBC Specific Gravity Urobilinogen pH

